## Study design

This randomized split-mouth clinical trial included 13 systemically healthy adults with a total of 65 papilla deficiencies in the aesthetic zone. The study was approved by the Altınbaş University Ethics Committee. All participants provided written informed consent.

Inclusion criteria required  $\geq 2$  papillae classified as Papilla Presence Index (PPI) class 2 or 3, probing depths  $\leq 3$  mm, and plaque and bleeding scores below 15%. Exclusion criteria included PPI class 4, diastema, active periodontal disease, smoking, pregnancy, systemic conditions influencing healing, anticoagulant use, and previous surgical papilla reconstruction.

For each participant, one side was randomly assigned HA and the contralateral side i-PRF. The clinical examiner underwent intra-examiner calibration until repeated measurements were consistent within  $\pm 1$  mm. Outcome assessments were performed by a blinded examiner.

For i-PRF sites, 10–20 mL of venous blood was collected into plastic tubes and centrifuged at 700 rpm for 3 minutes. The upper orange plasma layer was aspirated and transferred to 1-mL insulin syringes. Injections were delivered within 5 minutes to ensure liquid consistency before polymerization.

All treatments were performed with buccal infiltration anesthesia. HA or i-PRF (0.1–0.2 mL) was injected from the buccal aspect, 2–3 mm apical to the papilla tip, at a 45° angle. A single

puncture per session was used to minimize trauma. Slight blanching indicated correct placement. Each papilla received three injections at baseline, week 3, and week 6.

Participants avoided mechanical oral hygiene for 24 hours and interdental brushes for one week, replacing them with 0.12% chlorhexidine rinses. Modified Bass brushing resumed the following day.

Standardized photographs were obtained using a custom photograph standardization device (PSD), enabling consistent image acquisition. Black triangle height (BTH), width (BTW), area (BTA), and papilla height (PH) were measured at baseline, 1 month, and 3 months using ImageJ. PPI was recorded visually. Radiographs were taken to measure the distance between the interdental bone crest and contact point (IBC-ICP). Keratinized tissue thickness (KTT) was measured at baseline.

Pain was assessed after each injection using a VAS scale from 0 (none) to 10 (worst). Aesthetic satisfaction was rated at each visit using a VAS scale from 0 (not satisfied) to 10 (highly satisfied).

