## Statistical Analysis Plan

The data were analysed using the Statistical Package for the Social Sciences (SPSS) version 26.0. The normality of distribution for the numerical variables related to the patients and the evaluated interdental papilla sites was assessed based on skewness and kurtosis values. Normality of continuous data will be assessed using the Shapiro–Wilk test and visual inspection of Q–Q plots. A reference range of  $\pm 1.96$  was adopted as the criterion for normal distribution (Kalayci, 2005).

For each material, changes over time from baseline to follow-up will be analysed using repeated-measures ANOVA when assumptions are met, or the Friedman test in the case of non-parametric or ordinal data. Post-hoc pairwise comparisons between time points will include Bonferroni adjustments. Since the study design is split-mouth, inter-group comparisons between HA and i-PRF at each time point, as well as comparisons of change scores, will use paired t-tests for normally distributed variables and Wilcoxon signed-rank tests otherwise. PPI, being ordinal, will be evaluated with non-parametric paired procedures. Subgroup analyses will be performed separately for maxillary and mandibular papillae using similar paired or repeated-measures methods. Patient-reported VAS outcomes will be analysed using repeated-measures methods for within-group changes and paired testing for between-group differences.

Comparisons of KTT and IBC-ICP measurements across jaw localizations and treatment groups, as well as intergroup analyses of clinical outcome variables, were performed using the One-Way ANOVA test. Intragroup comparisons of variables measured at different time points were conducted using the Repeated Measures ANOVA. Where applicable, Post Hoc tests were employed to further investigate significant intergroup differences.

Additionally, to evaluate the relationship between KTT and IBC-ICP measurements and the percentage changes in clinical parameters, the Spearman correlation test was used. In interpreting the correlation coefficients, a range of 0.00–0.30 was considered low, 0.30–0.70 moderate, and 0.70–1.00 high. A significance level of  $p < 0.05$  and  $p < 0.01$  was adopted for all statistical analyses.

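### The Spearman correlations of KTT and IBC-ICP with percentage change have no patient or jaw term, so they are unreliable if predictor and response both cluster by mouth or both differ by jaw

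*Combined protocol and SAP*

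**What the plan says.** The Study design section reports "13 systemically healthy adults with a total of 65 papilla deficiencies in the aesthetic zone". Within each patient, "one side was randomly assigned HA and the contralateral side i-PRF". Black triangle dimensions, papilla height and the crest-to-contact distance are described there as site measurements.

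The last paragraph of the Statistical Analysis Plan gives the method for the correlations in one sentence: "to evaluate the relationship between KTT and IBC-ICP measurements and the percentage changes in clinical parameters, the Spearman correlation test was used". It then sets strength bands, under which "a range of 0.00–0.30 was considered low, 0.30–0.70 moderate, and 0.70–1.00 high", and significance levels of 0.05 and 0.01. It does not name the unit of analysis, and it mentions no patient effect, jaw adjustment, stratification or confidence interval.

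Elsewhere the same section does recognise both structures. Pairing within the mouth is used for the HA versus i-PRF comparisons. Jaw appears in the one-way ANOVA, which covers "Comparisons of KTT and IBC-ICP measurements across jaw localizations and treatment groups", and in the subgroup plan: "Subgroup analyses will be performed separately for maxillary and mandibular papillae using similar paired or repeated-measures methods". Neither provision extends to the correlations.

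**The concern.** An ordinary Spearman test takes its null distribution from independent pairs of values. Papillae from one mouth share tissue type, oral hygiene, healing and the operator's technique, so both the predictor and the response may be more alike within a patient than between patients. The effective number of observations is then below 65, and the p-value is too small.

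Jaw raises a separate problem. If KTT or IBC-ICP differs between maxilla and mandible, and the percentage change does too, a coefficient pooled over jaws is non-zero even when the two are unrelated within each jaw. That is bias in the coefficient itself, and more papillae would not remove it.

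The trial could therefore report tissue thickness or crest distance as significantly or moderately related to papilla fill when the association reflects the jaw the papillae came from, or rests on 13 patients while being tested as 65 independent sites.

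**Working it through.** The plan states no ICC, correlation or jaw difference, so there is no figure of its own to reproduce. The reference points are its 0.05 level (taken as two-sided, since sidedness is not stated) and its 0.30 cut-off for a moderate coefficient.

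**Inputs from the documents.** 13 patients and 65 papillae, so 65/13 = 5 per patient, or about 2.5 per patient and material.

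**Inputs assumed.** ICC from 0 to 0.7, equal in predictor and response unless stated. Jaw shift from 0 to 1.5 within-jaw SD, the same in both variables unless stated, with papillae split about evenly by jaw within each patient. There is no true relation within patient and jaw. Simulated rates use 20,000 runs per setting (Monte Carlo error about 0.2 points at a 5% rate).

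**1. Reference.** The critical value is |rho| = t/√(n − 2 + t²). For n = 65, t = 1.998 on 63 df, giving 1.998/√(63 + 3.993) = 0.244. For the patient as unit, n = 13 and t = 2.201 on 11 df, giving 2.201/√(11 + 4.844) = 0.553. With independent papillae the simulation rejects in 5.1%, and |rho| reaches 0.30 in 1.6%.

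**2. Clustering only.** The variance of the coefficient is inflated by about 1 + (m − 1) × ICC(predictor) × ICC(response). With m = 5 and ICC 0.5 in both, this is 1 + 4 × 0.25 = 2.0. The effective cut-off is 1.96/√2.0 = 1.386, and the type I error about 16.6%. The simulation on ranks gives slightly less:

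| ICC in both | Variance factor | Approximate type I error | Simulated p<0.05 | Simulated abs(rho) ≥ 0.30 |
|---|---|---|---|---|
| 0.1 | 1.04 | 5.5% | 5.3% | 1.7% |
| 0.2 | 1.16 | 6.9% | 6.5% | 2.3% |
| 0.3 | 1.36 | 9.3% | 8.6% | 3.4% |
| 0.5 | 2.00 | 16.6% | 15.2% | 7.4% |
| 0.7 | 2.96 | 25.5% | 25.3% | 15.8% |

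- Unequal numbers per patient (2 to 8) raise the rate to 9.5%, 17.3% and 27.9% at ICC 0.3, 0.5 and 0.7.
- Within one material (32 papillae) it falls to 6.5%, 9.5% and 13.9%. With so few papillae, however, |rho| reaches 0.30 in 9.6% even at ICC 0.
- With ICC 0.5 in one variable and 0 in the other, the factor is 1 + 4 × 0 = 1, and the simulated rate is 5.2%.

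**3. Jaw shift only (ICC 0).** With half the papillae in each jaw, no relation within jaw, and shifts of d₁ and d₂ SD in the two variables, the expected Spearman coefficient is 3 × [Φ(d₁/√2) − 0.5] × [Φ(d₂/√2) − 0.5]. At 1.0 SD in both, Φ(0.707) = 0.760, so rho = 3 × 0.260² = 0.20.

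| Shift in both (SD) | Expected rho | Simulated p<0.05 | Simulated abs(rho) ≥ 0.30 |
|---|---|---|---|
| 0.5 | 0.06 | 7.6% | 2.8% |
| 0.8 | 0.14 | 19.2% | 9.0% |
| 1.0 | 0.20 | 37.6% | 21.5% |
| 1.3 | 0.31 | 72.8% | 54.4% |
| 1.5 | 0.38 | 89.6% | 77.8% |

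If either shift is zero, the product is zero. The simulated rate with a 1.5 SD shift in one variable only is 5.0%.

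**4. Both together.** ICC 0.3 with a 0.8 SD shift gives p<0.05 in 22.2%. ICC 0.5 with a 1.0 SD shift gives 42.9%.

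**5. Does adjustment repair it?** Regressing the ranks on patient (fixed effects) and jaw, then testing the correlation of the residuals on 65 − 14 − 1 = 50 df, gave 4.5% to 5.3% in every setting. Material and the mixed-model option were not part of this check.

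**The case against.** Four objections carry weight.

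**The unit is inferred.** The SAP does not say that the correlations are run on papillae. The inference rests on the measurements being made per site and is the natural reading, but it remains an inference. If the correlations are run within jaw, the jaw part does not apply. If they are run per material, the clustering part is smaller.

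**A planned comparison is not an expected difference.** A reader might infer from the ANOVA by jaw that the SAP expects KTT and IBC-ICP to differ between jaws. It does not say so. The same sentence also compares them between the treated sides, where randomisation gives no reason to expect a difference. The text allows for a jaw difference and no more.

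**The inflation needs both variables.** A reader might infer that clustering or a jaw difference in KTT or IBC-ICP is enough. It is not, and modest values do little. With ICC 0.5 in the predictor but 0.1 in the response, the factor is 1 + 4 × 0.05 = 1.2, and the type I error about 7.4%.

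**The reach is limited, and some between-patient association may be real.** The correlations are introduced as an addition and described as a relationship, not as prediction. If patients with thicker tissue respond better, that is a genuine finding, though one supported by 13 patients.

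All four stand as limits on the size and wording of the point. None supplies the missing patient or jaw term.

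**Conclusion.** Wrong as written; the SAP should be changed. It specifies a test for independent observations for measurements that come, on the natural reading, from 65 papillae in 13 patients, with no patient or jaw term.

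The size depends on quantities the documents do not give. Clustering in both variables is negligible at ICC 0.1 and takes the 5% test to about 9% at 0.3, 15% at 0.5 and 25% at 0.7. A jaw shift in both variables matters little at 0.5 SD. It makes a moderate label the expected result only from about 1.3 SD. With clustering or a shift in one variable only, the error rate stays near 5%.

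A reader might infer that the correlations will be falsely positive, or that the trial's main conclusion is at risk. The documents support neither. The first depends on unknown ICCs and jaw differences; the second fails because the HA versus i-PRF comparison does not use these coefficients.

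**What to change.** In the last paragraph of the Statistical Analysis Plan:

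- State that the papilla is the unit of analysis, with 65 papillae in 13 patients.
- Replace the simple Spearman test with a rank-based analysis of the same outcome, percentage change, adjusted for patient, jaw and material. Patient can enter as fixed effects on the ranks. Alternatively, use a mixed model with a random patient effect that separates within-patient from between-patient values of KTT and IBC-ICP. A partial Spearman coefficient adjusted only for jaw and material would not do, because patient differences stay in the coefficient.
- Report a 95% CI that respects the 13 patients, for example by resampling patients, beside any low, moderate or high label. Do not require the interval to lie wholly inside a band. Even with 65 independent papillae, Fisher's half-width is 1.96/√62 = 0.249, so rho = 0.50 has an interval of 0.29 to 0.66, and only rho of about 0.51 to 0.55 would earn the moderate label.
- Call the analysis exploratory.

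The cost is SAP wording and a modest re-analysis of data already collected. Intervals will be wider and fewer associations significant. With patient, jaw and material as fixed effects, 65 − 15 − 1 = 49 df remain. The critical partial coefficient rises from 0.244 to 2.010/√(49 + 4.038) = 0.276. The fixed-effects version also says nothing about differences between patients; the mixed model does, but with only 13 patients to support it.

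### Correlating IBC-ICP (and, conditionally, KTT) with percentage change without adjusting for baseline can produce an association when anatomy has no effect on the gain

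*Combined protocol and SAP*

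**What the plan says.** The last paragraph of the Statistical Analysis Plan adds an association analysis: "to evaluate the relationship between KTT and IBC-ICP measurements and the percentage changes in clinical parameters, the Spearman correlation test was used". It then bands the coefficients as low (up to 0.30), moderate (0.30–0.70) and high (above 0.70).

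The Study design section supplies the ingredients:
- Black triangle height (BTH), width (BTW) and area (BTA) and papilla height (PH) "were measured at baseline, 1 month, and 3 months using ImageJ".
- IBC-ICP is the radiographic "distance between the interdental bone crest and contact point (IBC-ICP".
- "Keratinized tissue thickness (KTT) was measured at baseline".
- The sample is "13 systemically healthy adults with a total of 65 papilla deficiencies in the aesthetic zone".
- Eligible sites are "papillae classified as Papilla Presence Index (PPI) class 2 or 3", so baseline size varies between sites.

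The plan gives no formula or time point for percentage change and does not list the clinical parameters meant. It specifies no baseline adjustment, partial correlation or regression for this analysis. The change scores it mentions elsewhere belong to the HA versus i-PRF comparison. On the Papilla Presence Index it says: "PPI, being ordinal, will be evaluated with non-parametric paired procedures".

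**The concern.** A percentage change carries its baseline value in the denominator. If two sites gain the same amount, the one with the smaller initial defect shows the larger percentage. Any anatomical measure that tracks initial size can therefore correlate with percentage change whether or not it influences the gain.

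IBC-ICP is a plausible candidate by geometry, because the papilla and the open space above it both lie between bone crest and contact point. At stake is whether the trial reports bone-to-contact distance as related to treatment response when part or all of the coefficient comes from the choice of scale. At the upper end of the plausible range, the spurious coefficient falls in the band that the plan itself labels moderate.

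**Working it through.** The plan gives no sample-size, power or correlation figure for this analysis, so there is nothing to reproduce. The check asks how often the planned test is significant when anatomy has no effect on the gain.

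**1. Formula.** Percentage change = 100 × (baseline − follow-up) / baseline = 100 × gain / baseline. Put mean baseline at 1 and gain at 0.3 for every site. With baseline CV 0.5, a site one SD below the mean shows 0.3/0.5 = 60% and one SD above shows 0.3/1.5 = 20%. The gain is identical.

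**2. Link between IBC-ICP and baseline.** As a simplification, write IBC-ICP = open space + soft tissue below the papilla tip, with the two parts uncorrelated. Then corr(IBC-ICP, open space) = 1/√(1 + k²), where k is the SD of the tissue part divided by the SD of the open space. A correlation of 0.7 needs k = √(1/0.49 − 1) ≈ 1.0; 0.5 needs k = √3 ≈ 1.7; 0.3 needs k = √(1/0.09 − 1) ≈ 3.2. The documents do not give k, so 0.3–0.7 is an assumption.

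**3. Simulation, gain independent of baseline.** From the documents: n = 65 sites and alpha 0.05 (taken as two-sided), giving a critical |r| of 0.244. Assumed: independent sites, log-normal baseline with CV 0.3–0.5, gain distributed N(0.4, 0.2) in units of median baseline and capped at baseline, no measurement error, 3,000 trials per setting.
- Percentage change: mean Spearman about -0.14 to -0.42, and p<0.05 in about 19–94% of trials (about 60% at CV 0.4 and correlation 0.5).
- Absolute change: about 5–7%.
- With no correlation between anatomy and baseline, the percentage-change rate is about 5%; at a correlation of 0.1 it is only about 6–7%.

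**4. Other inputs.** Mean gain 0.3 of mean baseline, gain CV 0.3, 5,000 trials. Entries are the share with p<0.05 for percentage change; ranges run from baseline CV 0.3 to 0.5.

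| Setting | corr. 0.3 | corr. 0.5 | corr. 0.7 |
|---|---|---|---|
| n = 65, error SD 0.1 of mean baseline | 19–30% | 45–68% | 73–94% |
| n = 65, no measurement error | 36–47% | 75–91% | 97–99.9% |
| n = 32 (about one material), CV 0.5, error SD 0.1 | 17% | 37% | 68% |
| PH-like: CV 0.2, gain 0.2 | 21% | 49% | 79% |

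In the first row the mean coefficients are -0.13 to -0.18, -0.22 to -0.29 and -0.31 to -0.42.

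**5. Gain proportional to baseline.** Percentage change now holds about 4–6% at every correlation. Unadjusted absolute change is inflated: about 18–95% over correlations 0.3–0.7. Absolute change also drifts when large gains are cut off by full closure: with mean gain 0.7, CV 0.5 and no measurement error, it gives 18%, 43% and 71% at correlations 0.3, 0.5 and 0.7.

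**6. Adjusting for baseline.** With baseline as a covariate, the rate is about 4–6% under both gain models when baseline is measured without error. With error SD 0.1 it is about 5–11% in the linear model. A rank partial correlation gives 6–25% under the inputs of step 4 with the same error. Error in the baseline thus leaves some confounding.

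**7. PPI.** A one-class gain is 1/2 = 50% from class 2 and 1/3 = 33% from class 3. The difference reflects only the numbering of the classes.

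**The case against.** The strongest reply is that the inflation rests on one gain model. The documents do not say that gain is independent of baseline. The background section speaks of partial or complete closure, for which the fraction filled is a natural scale. Under proportional gain, percentage change is the sound choice and absolute change the misleading one. This stands: the plan justifies neither model, and raw absolute change is not a remedy. It does not rescue an unadjusted percentage-change correlation, because adjustment for baseline performs acceptably under both models.

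Further limits also stand:
- IBC-ICP contains soft tissue as well as open space, so the size of its link with BTH is unknown. BTW is a width and does not lie along that distance.
- A reader might infer that KTT is equally affected. The documents give no basis for or against a link between KTT and baseline size, so for KTT the point is conditional.
- A reader might infer that the plan pools both materials. It is silent on this.
- A reader might infer that a percentage change in PPI will be calculated. The plan never says so; it only leaves the parameters unlisted.
- A reader might expect clustering of sites within participants always to raise the error rates. With an assumed intraclass correlation of 0.3, the null rate rose to about 9% and low-correlation rates rose, but rates at a correlation of 0.7 fell slightly.

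This is also a secondary analysis, outside the trial's hypothesis about the two materials.

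**Conclusion.** The concern holds in a conditional form. Without baseline adjustment, the planned correlation of IBC-ICP with percentage change can be significant when IBC-ICP has no effect on the gain. Two conditions are needed: IBC-ICP must be correlated with baseline size, and the gain must not scale with baseline. Under the first set of assumptions (step 3), the false-positive rate is about 19–94% instead of 5%. The width of that range reflects how little the documents say about baseline spread and the anatomy–baseline correlation. If either condition fails, the rate returns to about 5%.

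It would go too far to say that any observed coefficient reflects only the denominator. The documents fix neither the gain model nor the strength of the link, so the most that can be said is that it could partly or wholly do so. The change is worth making because it is cheap and does not require knowing which gain model is true.

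**What to change.** Replace the percentage-change correlations with a model for each continuous parameter, fitted at site level:

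3-month value = intercept + b1 × baseline value + b2 × anatomy (KTT or IBC-ICP) + b3 × material + random participant effect + error.

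The absolute change may be the response instead, provided baseline stays in the model. The random effect is needed because 65 sites come from 13 people. Report b2 with its 95% CI and label the analysis exploratory. List the parameters included. If PPI is among them, use change in class and compute no percentage.

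The cost is SAP wording and a few models on data already in the measurement plan. The result is less simple to present than one coefficient, and some residual confounding remains if baseline is measured with error; the report should say so.

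### Correlation strength is labelled low, moderate or high from the point estimate alone, with no interval and no allowance for several sites per participant; at these site counts the labels are unreliable in both directions

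*Combined protocol and SAP*

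**What the plan says.** The last paragraph of the Statistical Analysis Plan relates two baseline or anatomical measurements, KTT and IBC-ICP, to outcome: "the percentage changes in clinical parameters, the Spearman correlation test was used". The reading rule follows: "In interpreting the correlation coefficients, a range of 0.00–0.30 was considered low, 0.30–0.70 moderate, and 0.70–1.00 high". The only other guidance is a pair of significance levels, 0.05 and 0.01, which "was adopted for all statistical analyses". No interval or other measure of precision is planned for the coefficients, and no method is described for several sites in one mouth.

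The Study design section gives the size: "13 systemically healthy adults with a total of 65 papilla deficiencies in the aesthetic zone". It also states: "For each participant, one side was randomly assigned HA and the contralateral side i-PRF". The SAP does not say whether the correlations pool all 65 sites or are run per material. It plans jaw subgroups ("Subgroup analyses will be performed separately for maxillary and mandibular papillae") but does not say whether the correlations are split that way too.

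**The concern.** The bands are applied to an estimate as if it were the true coefficient. With 65 sites or fewer, sampling error is of the same order as the width of the low and moderate bands, so the word attached to a coefficient depends heavily on chance. Because sites in one mouth tend to resemble one another, the real uncertainty may be greater than 65 independent sites would suggest.

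At stake is how these results are read. A report that papilla gain is moderately related to KTT or IBC-ICP would give no sign that the same data also fit a weak relation. Equally, a label of low could hide a real moderate relation.

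**Working it through.** The documents give no sample size, power or precision figure for the correlations, so there is nothing to reproduce.

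**Inputs.** From the documents: 65 sites, 13 participants, cut-offs 0.30 and 0.70, levels 0.05 and 0.01. Assumed: two-sided tests; about 33 sites per material (65/2 = 32.5, not stated in the plan); true coefficients of 0.10, 0.20 and 0.40 as illustrations; independent sites in steps 1 to 3.

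**1. How often the label is wrong.** Bivariate normal data were simulated (40,000 runs per setting) and checked with Fisher's z, using SE = √(1.06/(n−3)). The SE is √(1.06/62) = 0.131 at n = 65 and √(1.06/30) = 0.188 at n = 33. On the z scale, 0.20, 0.30 and 0.40 become 0.203, 0.310 and 0.424.

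- True 0.20, n = 65: (0.310 − 0.203)/0.131 = 0.82, so about 21% reach 0.30; simulation 20%.
- True 0.20, n = 33: 0.107/0.188 = 0.57, so about 29% with both tails; simulation 28%.
- True 0.40, n = 65: (0.310 − 0.424)/0.131 = −0.87, so about 19% fall below 0.30; simulation 19%.
- True 0.40, n = 33: −0.114/0.188 = −0.61, so about 27%; simulation 27%.
- True 0.10: labelled at least moderate in 5% at n = 65 and 14% at n = 33 (simulation).

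**2. Intervals around an observed coefficient.** Fisher z with the Spearman variance (1 + r²/2)/(n−3). For r = 0.40, z = 0.424 and 1 + r²/2 = 1.08.

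- n = 65: SE = √(1.08/62) = 0.132; 0.424 ± 0.259 = 0.165 to 0.682; back-transformed, 0.16 to 0.59.
- n = 33: SE = √(1.08/30) = 0.190; 0.424 ± 0.372 = 0.052 to 0.796; back-transformed, 0.05 to 0.66.

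By the same formula, an observed 0.50 gives 0.28 to 0.67 at n = 65 and 0.17 to 0.73 at n = 33. An observed 0.60 gives 0.40 to 0.75 and 0.295 to 0.79. Every one of these intervals crosses at least one cut-off.

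**3. Where significance meets the 0.30 cut-off.** The smallest significant coefficient is t/√(n − 2 + t²), with t the two-sided quantile on n − 2 degrees of freedom (the usual approximation for Spearman).

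- n = 65: 1.998/√(63 + 3.993) = 0.244.
- n = 44: 2.018/√(42 + 4.073) = 0.297.
- n = 43: 2.020/√(41 + 4.079) = 0.301.
- n = 33: 2.040/√(31 + 4.160) = 0.344.
- n = 65 at the 0.01 level: 2.656/√(63 + 7.055) = 0.317.

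So with 43 sites or fewer, any coefficient with p < 0.05 exceeds 0.30 and is labelled at least moderate. With all 65 sites, significant coefficients from 0.244 up to 0.30 can still be labelled low.

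**4. Sensitivity to clustering.** With 13 participants and an assumed intraclass correlation of 0.5 on both variables (20,000 runs), a true 0.20 is labelled at least moderate in 28% at n = 65 and 31% at n = 33. With no true relation, a test that treats sites as independent gives p < 0.05 in about 15% of trials at n = 65 and 9% at n = 33.

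**The case against.** Fixed verbal bands are a common descriptive convention, and these correlations are introduced as additional analyses. The SAP speaks of a relationship, not of a prediction or selection rule. That is a fair reason to rank the point low. It does not remove it: the interval is the missing piece, and it costs almost nothing.

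Four stronger readings are tempting, and the documents do not support them.

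- **The rule builds in an upward exaggeration.** It does not. Step 1 shows errors in both directions at similar rates, and the mean estimate for a true 0.20 stays at about 0.20. Inflation appears only if attention is confined to significant coefficients: at n = 33 with a true 0.20 those average about 0.43. The SAP does not restrict the labels to significant results.
- **Every significant correlation must be at least moderate.** This depends on the number of sites. It is true at the 0.05 level up to 43 sites and not at 65, and the SAP does not say which count applies. Nothing in the plan describes a correlation on one value per participant, so thresholds for n = 13 are not relevant.
- **A moderate label would be equally compatible with no relation.** For an observed 0.40, both intervals in step 2 exclude zero. The data are imprecise, and also compatible with a weak relation, but not equally so.
- **The label would be used to choose sites for treatment.** Nothing in the documents says this.

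**Conclusion.** The concern holds in a limited form. The plan attaches a strength label to an estimate with no stated precision, and at 65 or about 33 sites the data often cannot tell low from moderate. For true values of 0.20 and 0.40 the label is wrong in roughly one trial in five with all sites pooled, and in more than one in four at about 33 sites. For a true 0.10 at 65 independent sites the rate is only 5%, so the size of the problem depends on a coefficient that nobody knows.

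The figures in steps 1 to 3 assume independent sites. Under the assumed clustering in step 4, over-labelling of a true 0.20 is more frequent and the unadjusted test gives too many false positives. The count of 33 and the intraclass correlation are assumptions, not figures from the plan. The HA versus i-PRF comparison is untouched, so this is a minor, worthwhile correction.

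**What to change.** In the last paragraph of the SAP:

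- State for each correlation which sites enter (pooled, per material or per jaw) and how many.
- Report each Spearman coefficient with a 95% confidence interval from a bootstrap that resamples participants, keeping all of a participant's sites together, and base the interpretation on that interval.
- Delete the low, moderate and high labels, or allow one only when the whole interval lies inside a single band. A looser rule that asks only for the interval to lie above a band's lower limit would not work, because the low band starts at 0 and every absolute coefficient meets it.

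The cost is a few lines of SAP text and a short bootstrap program; no new data are needed. There are two drawbacks. Few or no correlations will earn a label: in step 2, observed coefficients of 0.40, 0.50 and 0.60 would all go unlabelled at either site count. And with only 13 participants to resample, the bootstrap interval is itself approximate, which the report should say.
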